### 3.4.1 Immune-mediated AEs (imAEs)

Based on the mechanism of action of durvalumab and tremelimumab leading to T-cell activation and proliferation, there is the possibility of observing immune-mediated AEs (imAEs) during the conduct of this study. Potential imAEs may be similar to those seen with the use of ipilimumab, BMS-936558 (anti-PD-1 mAb), and BMS-936559 (anti-PD-L1 mAb) and may include immune-mediated enterocolitis, dermatitis, hepatitis (hepatotoxicity), and endocrinopathies[4, 34, 35]. These AEs are inflammatory in nature and can affect any organ.

Subjects should be monitored for signs and symptoms of imAEs. In the absence of an alternate etiology (e.g., infection or PD), an immune-mediated etiology should be considered for signs or symptoms of enterocolitis, dermatitis, hepatitis, and endocrinopathy. Dosing modification and management guidelines for imAEs specified in [Appendix F](#).

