### 3.4.2 Adverse Events of Special Interest

An adverse event of special interest (AESI) is one of scientific and medical interest specific to understanding of the investigational product and may require close monitoring and rapid communication by the investigator to the sponsor. An AESI may be serious or non-serious. The rapid reporting of AESIs allows ongoing surveillance of these events in order to characterize and understand them in association with the use of this investigational product.

AESIs for durvalumab and tremelimumab include but are not limited to events with a potential inflammatory or immune-mediated mechanism and which may require more frequent monitoring and/or interventions such as steroids, immunosuppressants and/or hormone replacement therapy. These AESIs are being closely monitored in clinical studies with durvalumab monotherapy and combination therapy. An immune-mediated adverse event (imAE) is defined as an adverse event that is associated with drug exposure and is consistent with an immune-mediated mechanism of action and where there is no clear alternate etiology. Serologic, immunologic, and histologic (biopsy) data, as appropriate, should be used to support an imAE diagnosis. Appropriate efforts should be made to rule out neoplastic, infectious, metabolic, toxin, or other etiologic causes of the imAE.

AESIs observed with durvalumab and tremelimumab include:

- Diarrhea / Colitis and intestinal perforation
- Pneumonitis / ILD
- Hepatitis / transaminase increases
- Endocrinopathies (i.e. events of hypophysitis/hypopituitarism, adrenal insufficiency, hyper- and hypothyroidism and type I diabetes mellitus)
- Rash / Dermatitis
- Nephritis / Blood creatinine increases
- Pancreatitis / serum lipase and amylase increases
- Myocarditis
- Myositis / Polymyositis
- Neuropathy / neuromuscular toxicity (i.e. Guillain-Barre, and myasthenia gravis)
- Other inflammatory responses that are rare / less frequent with a potential immune-mediated etiology include, but are not limited to, pericarditis, sarcoidosis, uveitis and other events involving the eye, skin, hematological and rheumatological events, vasculitis, non-infectious meningitis and non-infectious encephalitis.

For current list of adverse drug reactions (ADR)s for durvalumab, please, see [Appendix G](#)

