#### **3.8.1 Criteria for Removal from Protocol Therapy**

An individual subject will not receive any further investigational product if any of the following occur in the subject in question:

- Pregnancy or intent to become pregnant
- Any AE that meets criteria for discontinuation as defined in section 3.4.
- Patient decides to withdraw from the study
- Adverse event related to durvalumab or tremelimumab, with the exception of toxicities that do not meet the criteria for discontinuation as defined in section 3.4 if applicable
- Grade  $\geq 3$  infusion reaction
- Initiation of alternative anticancer therapy including another investigational agent
- Confirmation of PD and investigator determination that the subject is no longer benefiting from treatment with durvalumab + tremelimumab
- Investigator discretion

Subjects who are permanently discontinued from further receipt of investigational product, regardless of the reason (withdrawal of consent, due to an AE, other), will be identified as having permanently discontinued treatment.

Subjects who are permanently discontinued from receiving investigational product will be followed for safety per Section 7, including the collection of any protocol-specified blood specimens, unless consent is withdrawn or the subject is lost to follow-up or enrolled in another clinical study. Subjects who decline to return to the site for evaluations will be offered follow-up

by phone every 3 months as an alternative. All subjects will be followed for survival by phone call or e-mail every 6 months.

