
**Abbreviated Title: Immune Checkpoint Inhibition**

**Version Date: 04/28/21**

Grade 3 Depending on the individual toxicity, study drug/study regimen may be permanently discontinued. Please refer to guidelines below.
 
Grade 4 Permanently discontinue study drug/study regimen.
 
Note: For asymptomatic amylase or lipase levels of >2X ULN, hold study drug/study regimen, and if complete work up shows no evidence of pancreatitis, study drug/study regimen may be continued or resumed.
 
Note: Study drug/study regimen should be permanently discontinued in Grade 3 events with high likelihood for morbidity and/or mortality – e.g., myocarditis, or other similar events even if they are not currently noted in the guidelines. Similarly, consider whether study drug/study regimen should be permanently discontinued in Grade 2 events with high likelihood for morbidity and/or mortality – e.g., myocarditis, or other similar events even if they are not currently noted in the guidelines – when they do not rapidly improve to Grade <1 upon treatment with systemic steroids and following full taper
 
Note: There are some exceptions to permanent discontinuation of study drug for Grade 4 events (i.e., hyperthyroidism, hypothyroidism, Type 1 diabetes mellitus).
	
taper).
 
– More potent immunosuppressives such as TNF inhibitors (e.g., infliximab; also refer to the individual sections of the imAEs for specific type of immunosuppressive) should be considered for events not responding to systemic steroids. Progression to use of more potent immunosuppressives should proceed more rapidly in events with high likelihood for morbidity and/or mortality – e.g., myocarditis, or other similar events even if they are not currently noted in the guidelines – when these events are not responding to systemic steroids.
 
– With long-term steroid and other immunosuppressive use, consider need for Pneumocystis jirovecii pneumonia (PJP), formerly known as Pneumocystis carinii pneumonia) prophylaxis, gastrointestinal protection, and glucose monitoring.
 
– Discontinuation of study drug/study regimen is not mandated for Grade 3/Grade 4 inflammatory reactions attributed to local tumor response (e.g., inflammatory reaction at sites of metastatic disease and lymph nodes). Continuation of study drug/study regimen in this situation should be based upon a benefit-risk analysis for that patient.

--	--

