
Diarrhea/Colitis Large intestine perforation/Intestine perforation
	
Any Grade
	
Grade 1 (Diarrhea: stool frequency of <4 over baseline per day) (Colitis: asymptomatic; clinical or diagnostic observations only;
	
General Guidance
	
infiximab.
 
 
- Once the patient is improving, gradually taper steroids over <math>\geq 28</math> days and consider prophylactic antibiotics, antifungals, and, in particular, anti-PJP treatment (refer to current NCCN guidelines for treatment of cancer-related infections).a
 
 
For Any Grade:
 
 
- Monitor for symptoms that may be related to diarrhea/enterocolitis (abdominal pain, cramping, or changes in bowel habits such as increased frequency over baseline or blood in stool) or related to bowel perforation (such as sepsis, peritoneal signs, and ileus).
 
- When symptoms or evaluation indicate a perforation is suspected, consult a surgeon experienced in abdominal surgery immediately without any delay.
 
- PERMANENTLY DISCONTINUE STUDY DRUG FOR ANY GRADE OF INTESTINAL PERFORATION
 
- Patients should be thoroughly evaluated to rule out any alternative etiology (e.g., disease progression, other medications, or infections), including testing for clostridium difficile toxin, etc.
 
- Steroids should be considered in the absence of clear alternative etiology, even for low-grade events, in order to prevent potential progression to higher grade event, including perforation.
 
- Use analgesics carefully; they can mask symptoms of perforation and peritonitis.
 
 
For Grade 1:
 
 
- Monitor closely for worsening symptoms.
 
- Consider symptomatic treatment, including hydration, electrolyte replacement, dietary changes (e.g., American Dietetic Association colitis diet), loperamide and other supportive care measures.
 
- If symptoms persist consider checking lactoferrin; if positive treat as
 

---	-------------------------	--	--------------------------------	---

	intervention not indicated)		Grade 2 below. If negative and no infection, continue Grade 1 management .

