
Grade 2 (Diarrhea: stool frequency of 4 to 6 over baseline per day; limiting instrumental ADL) (Colitis: abdominal pain; mucus or blood in stool) (Perforation: invasive intervention not indicated)
	
Hold study drug/study regimen until resolution to Grade <math>\leq 1</math>
 
 
• If toxicity worsens, then treat as Grade 3 or Grade 4.
 
• If toxicity improves to Grade <math>\leq 1</math>, then study drug/study regimen can be resumed after completion of steroid taper.
 
		
For Grade 2:
 
 
– Consider symptomatic treatment, including hydration, electrolyte replacement, dietary changes (e.g., American Dietetic Association colitis diet), and loperamide and/or budesonide.
 
– Promptly start prednisone 1 to 2 mg/kg/day PO or IV equivalent.
 
– If event is not responsive within 2 to 3 days or worsens despite prednisone at 1 to 2 mg/kg/day PO or IV equivalent, GI consult should be obtained for consideration of further workup, such as imaging and/or colonoscopy, to confirm colitis and rule out perforation, and prompt treatment with IV methylprednisolone 2 to 4 mg/kg/day started.
 
– If still no improvement within 2 to 3 days despite 1 to 2 mg/kg IV methylprednisolone, promptly start immunosuppressives such as infliximab at 5 mg/kg IV, may be repeated at 2 and 6 weeks after initial dose at the discretion of the treating provider . Caution: it is important to rule out bowel perforation and refer to infliximab label for general guidance before using infliximab.
 
– Consider, as necessary, discussing with study physician if no resolution to Grade <math>\leq 1</math> in 3 to 4 days.
 
– Once the patient is improving, gradually taper steroids over <math>\geq 28</math> days and consider prophylactic antibiotics, antifungals, and anti-PJP treatment (refer to current NCCN guidelines for treatment of cancer-related infections).a
 

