
Grade 3 or 4 (Grade 3 Diarrhea: stool frequency of <math>\geq 7</math> over baseline per day;
	
Grade 3 - For patients treated with PD-1 or PDL-1 inhibitors, hold study drug/study regimen until resolution to Grade <math>\leq 1</math>; study drug/study regimen can be resumed
		
For Grade 3 or 4:
 
 
– Promptly initiate empiric IV methylprednisolone 1 to 2 mg/kg/day or equivalent.
 
– Monitor stool frequency and volume and maintain hydration.
 

	
limiting self care ADL; Grade 4 Diarrhea: life threatening consequences) (Grade 3 Colitis: severe abdominal pain, fever; ileus; peritoneal signs; Grade 4 Colitis: life-threatening consequences, urgent intervention indicated) (Grade 3 Perforation: invasive intervention indicated; Grade 4 Perforation: life-threatening consequences; urgent intervention indicated)
	
after completion of steroid taper. Permanently discontinue study drug/study regimen for Grade 3 if toxicity does not improve to Grade <math>\leq 1</math> within 14 days. - Permanently discontinue study drug for 1) Grade 3 colitis in patients treated with CTLA-4 inhibitors or 2) Any grade large intestine perforation/Intestinal perforation in any patient treated with ICI.
 
Grade 4 Permanently discontinue study drug/study regimen.
	
 
- Urgent GI consult and imaging and/or colonoscopy as appropriate.
 
- If still no improvement within 2 days, continue steroids and promptly add further immunosuppressant agents (e.g., infliximab at 5 mg/kg IV, may be repeated at 2 and 6 weeks after initial dose at the discretion of the treating provider)). Caution: Ensure GI consult to rule out bowel perforation and refer to infliximab label for general guidance before using infliximab. If perforation is suspected, consult a surgeon experienced in abdominal surgery immediately without any delay .
 
- Once the patient is improving, gradually taper steroids over <math>\geq 28</math> days and consider prophylactic antibiotics, antifungals, and anti-PJP treatment (refer to current NCCN guidelines for treatment of cancer-related infections).a
 

--	---	---	---

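### Appendix F's Grade 2 diarrhea/colitis/perforation row allows drug to be restarted after a perforation, although the same block requires permanent discontinuation at any grade

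*Combined protocol and SAP*

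**What the plan says.** The block in Appendix F (section 16.6) covers diarrhea, colitis and intestinal perforation together. Three places in it bear on perforation:

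- **Any Grade, toxicity management:** "PERMANENTLY DISCONTINUE STUDY DRUG FOR ANY GRADE OF INTESTINAL PERFORATION".
- **Grade 2:** the severity cell defines diarrhea, colitis and perforation, the last as "Perforation: invasive intervention not indicated". One dose-modification cell serves all three events. It says to hold until Grade 1 or lower; if the toxicity improves that far, "then study drug/study regimen can be resumed after completion of steroid taper".
- **Grade 3 or 4, dose modification:** the Grade 3 text lists among the reasons for permanent discontinuation "Any grade large intestine perforation/Intestinal perforation in any patient treated with ICI".

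The General Considerations at the head of Appendix F add a softer instruction for dangerous Grade 2 events: "Similarly, consider whether study drug/study regimen should be permanently discontinued in Grade 2 events with high likelihood for morbidity and/or mortality".

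Appendix F governs dosing. Section 3.4.1 reads "Dosing modification and management guidelines for imAEs specified in" Appendix F, and section 3.8.1 makes one criterion for removal from therapy "Any AE that meets criteria for discontinuation as defined in section 3.4".

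**The concern.** An investigator who looks up the dosing action for a Grade 2 perforation goes to the Grade 2 row, finds the event named there, and reads that drug may be restarted after the taper. The same block forbids that restart.

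The event is serious. Section 3.4.2 lists "Diarrhea / Colitis and intestinal perforation" among the adverse events of special interest. Section 3.4.2.5 says that colon perforation, though rare, may need surgery and may be fatal if poorly managed. What is at stake is re-exposing a patient to checkpoint inhibitors that the protocol means to stop for good. The primary endpoint, the sample size and the tests in section 10 are not involved.

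**Working it through.** The plan gives no figure to reproduce. The check is a comparison of cells, followed by a rough count of how often the cell could matter.

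**1. Instructions for a Grade 2 perforation**

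| Place in Appendix F | Names perforation? | Action |
|---|---|---|
| General Considerations, Grade 2 | No; refers to high-risk events generally | Hold, then may resume; consider stopping permanently if there is no rapid improvement |
| Block, Any Grade, management column | Yes | Stop permanently |
| Block, Grade 2, dose column | Yes, in the paired severity cell | Hold, then may resume after taper |
| Block, Grade 3 text, dose column | Yes, at any grade | Stop permanently |

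The second and fourth rows agree. The third permits what they prohibit, and the first does not settle the matter because it only asks the investigator to consider stopping.

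**2. Is the row intact?** Yes. The Grade 2 definitions and their dose cell sit together and are complete, so the conflict does not come from a broken table.

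**3. Does the any-grade rule apply to everyone?** Yes. Durvalumab and tremelimumab are both checkpoint inhibitors, so the wording about patients treated with an ICI covers all arms.

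**4. Where would a reader look?** The capitalised rule is in the management column; the Any Grade dose cell carries only a general heading. In the dose column the rule appears only within the Grade 3 text. A reader going across the Grade 2 row does not meet it.

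**5. Does the wrong cell reach a decision?** Section 3.8.1 exempts drug-related toxicities that do not meet the section 3.4 discontinuation criteria. Judged by its own Grade 2 cell, a Grade 2 perforation would fall within that exemption.

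**6. How often could it arise?** The documents give no perforation rate. Assume a per-patient probability p of a perforation of any grade between 0.001 and 0.01. The planned number is 10 + 30 + 30 = 70, and the accrual ceiling in section 10 is 90. Expected events are n × p, and the chance of at least one is 1 − (1 − p)^n.

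| n | p | Expected | Chance of at least one |
|---|---|---|---|
| 70 | 0.001 | 0.07 | 1 − 0.999^70 = 6.8% |
| 70 | 0.01 | 0.70 | 1 − 0.99^70 = 50.5% |
| 90 | 0.001 | 0.09 | 1 − 0.999^90 = 8.6% |
| 90 | 0.01 | 0.90 | 1 − 0.99^90 = 59.5% |

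These counts are for all grades. Only Grade 2 perforations meet the faulty cell, and the documents do not give their share, so each line is an upper limit on exposure for its assumed p.

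**The case against.** The strongest reply is that the block already deals with perforation, twice and once in capitals, and that any grade includes Grade 2. Appendix F often places such a rule above the graded cells without repeating it: transverse myelitis, confirmed SJS/TEN/SCAR and biopsy-proven myocarditis all end treatment, while graded cells in the same sections allow hold or restart. The Grade 2 wording is also permissive, so a site that stops drug breaks no rule. The row looks written for diarrhea and colitis: the Grade 1 cell defines no perforation, and the Grade 2 management text treats perforation as something to exclude. Harm would need a Grade 2 perforation, recovery, a completed taper of at least 28 days, and an investigator who missed the rule throughout.

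Much of this stands. The intended rule is clear and the failure path is narrow, which is why the point is minor. The parallels fail on one detail: those graded cells do not name the event covered by the overriding rule, whereas this one does. The cell is wrong about an event it expressly covers, which is worse than silence. A permission to resume still authorises what the other text forbids.

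The objection to the size also has force. The assumed range covers every grade, and its upper end is high beside Appendix G, where colitis of any grade on durvalumab alone was 28/3006 = 0.9% and perforation is not listed. Tremelimumab could raise the rate, but the documents do not say by how much. The upper figures should be read as a ceiling.

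Finally, Appendix F is a dated guideline (14 October 2020) for durvalumab alone or in combination, so editing it would make the protocol's copy differ from that text. That is a reason to mark the change clearly; it does not justify leaving the conflict. Section 3.4.2.4 already adds trial-specific caveats to Appendix F for liver tests.

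**Conclusion.** The concern holds as a minor error in the text. The Grade 2 dose-modification cell gives the wrong action for perforation, contrary to two explicit statements in the same block. This conclusion rests on the wording alone and needs no assumed rate.

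The practical effect is small. Fewer than one perforation of any grade is expected even at the assumed 1% rate and the 90-patient ceiling, only a Grade 2 case would meet the faulty cell, and most sites would follow the capitalised rule. The residual risk is a site that reads only the Grade 2 row. Correction is worthwhile because the event can be fatal and the permission runs in the unsafe direction.

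**What to change.** In the Grade 2 dose-modification cell, limit the hold-and-resume instruction to diarrhea and colitis, and add a line saying that perforation of any grade requires permanent discontinuation of the study regimen. This applies the protocol's own rule where a reader would look for it. If the sponsor prefers to leave the dated guideline untouched, one overriding sentence in section 3.4.2.5 would serve, as section 3.4.2.4 does for liver tests, but the cell itself is the better place.

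The cost is one table cell at the next amendment, with no change to design, sample size or analysis.

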	Grade 2 (symptomatic; medical intervention indicated; limiting instrumental ADL)	Hold study drug/study regimen dose until Grade 2 resolution to Grade $\leq 1$ . 
 
If toxicity worsens, then treat as Grade 3 or Grade 4.
 
If toxicity improves to Grade <math>\leq 1</math>, then the decision to reinitiate study drug/study regimen will be based
 
	
For Grade 2 (mild to moderate new symptoms):
 
 
Monitor symptoms daily and consider hospitalization.
 
Promptly start systemic steroids (e.g., prednisone 1 to 2 mg/kg/day PO or IV equivalent).
 
Reimage as clinically indicated, consider Chest CT with contrast and repeat in 3-4 weeks.
 
	

		
upon treating physician's clinical judgment and after completion of steroid taper.
	
 
- If no improvement within 2 to 3 days, additional workup should be considered and prompt treatment with IV methylprednisolone 2 to 4 mg/kg/day started
 
- If still no improvement within 2 to 3 days despite IV methylprednisolone at 2 to 4 mg/kg/day, promptly start immunosuppressive therapy such as TNF inhibitors (e.g., infliximab at 5 mg/kg IV once, may be repeated at 2 and 6 weeks after initial dose at the discretion of the treating provider ). Caution: It is important to rule out sepsis and refer to infliximab label for general guidance before using infliximab.
 
- Once the patient is improving, gradually taper steroids over ≥28 days and consider prophylactic antibiotics, antifungals, or anti-PJP treatment (refer to current NCCN guidelines for treatment of cancer-related infections)a
 
- Consider Pulmonary and Infectious Disease consults.
 
- Consider, as necessary, discussing with study physician.
 

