
Grade 2 (AST or ALT >3.0<math>\times</math>ULN and <math>\leq 5.0 \times</math>ULN if baseline normal, >3-5<math>\times</math>baseline if baseline abnormal; and/or TB >1.5<math>\times</math>ULN and <math>\leq 3.0 \times</math>ULN if baseline normal, >1.5-3.0<math>\times</math>baseline if baseline abnormal)
	
 
Permanently discontinue study drug/study regimen for any case meeting Hy's law criteria (AST and/or ALT >3 <math>\times</math> ULN + bilirubin >2 <math>\times</math> ULN without initial findings of cholestasis (i.e., elevated alkaline P04) and in the absence of any alternative cause.
 
	
For Grade 2:
 
 
Regular and frequent checking of LFTs (e.g., every 1 to 2 days) until elevations of these are improving or resolved.
 
If no resolution to <math>\leq</math>Grade 1 in 1 to 2 days, consider, as necessary, discussing with study physician.
 
If event is persistent (>2 to 3 days) or worsens, promptly start prednisone 1 to 2 mg/kg/day PO or IV equivalent.
 
If still no improvement within 3 to 5 days despite 1 to 2 mg/kg/day of prednisone PO or IV equivalent, consider additional work up and start prompt treatment with IV methylprednisolone 2 to 4 mg/kg/day.
 
If still no improvement within 3 to 5 days despite 2 to 4 mg/kg/day of IV methylprednisolone, promptly start immunosuppressives (i.e., mycophenolate mofetil).a Discuss with study physician if mycophenolate mofetil is not available. Infliximab should NOT be used.
 
Once the patient is improving, gradually taper steroids over <math>\geq 28</math> days and consider prophylactic antibiotics, antifungals, and anti-PJP treatment (refer to current NCCN guidelines for treatment of cancer-related infections).a
 

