
Isolated AST or ALT >5.0×ULN and <math>\leq 8.0 \times \text{ULN}</math>, if normal at baseline
 
Isolated AST or ALT >2.0×baseline and <math>\leq 12.5 \times \text{ULN}</math>, if elevated >ULN at baseline
	
 
Hold study drug/study regimen dose until resolution to AST or ALT <math>\leq 5.0 \times \text{ULN}</math>.
 
If toxicity worsens, then treat as described for elevations in the rows below.
 
If toxicity improves to AST or ALT <math>\leq 5.0 \times \text{ULN}</math>, resume study drug/study regimen after completion of steroid taper
 
	
 
Regular and frequent checking of LFTs (e.g., every 1 to 3 days) until elevations of these are improving or resolved.
 
Recommend consult hepatologist; consider abdominal ultrasound, including Doppler assessment of liver perfusion.
 
Consider, as necessary, discussing with study physician.
 
If event is persistent (>2 to 3 days) or worsens, and investigator suspects toxicity to be immune-mediated AE, recommend to start prednisone 1 to 2 mg/kg/day PO or IV equivalent.
 
If still no improvement within 2 to 3 days despite 1 to 2 mg/kg/day of prednisone PO or IV equivalent, consider additional workup and treatment with IV methylprednisolone 2 to 4 mg/kg/day.
 
If still no improvement within 2 to 3 days despite 1 to 2 mg/kg/day of IV methylprednisolone, consider additional abdominal workup (including liver biopsy) and imaging (i.e., liver ultrasound), and consider starting immunosuppressives (i.e., mycophenolate mofetil 0.5 – 1 g every 12 hours then taper in consultation with hepatology consult). Discuss with study physician if mycophenolate mofetil is not available. Infliximab should NOT be used.
 
	
Regular and frequent checking of LFTs (e.g., every 1-2 days) until

Isolated AST or ALT
	
 
Hold study drug/study regimen dose
 
	
Regular and frequent checking of LFTs (e.g., every 1-2 days) until
	

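### In two Appendix F rows (grade 2 diarrhea/colitis and the second transaminase level in HCC), the trigger for second-line immunosuppression names a methylprednisolone dose half that of the step before it

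*Combined protocol and SAP*

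**What the plan says.** Appendix F (section 16.6) sets out stepwise management of immune-mediated events. Two of its rows matter here.

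**Diarrhea/Colitis, Grade 2.**
- First steroid: "Promptly start prednisone 1 to 2 mg/kg/day PO or IV equivalent".
- If there is no response in 2 to 3 days, or the event worsens, a gastroenterology consult is obtained and the steroid is stepped up: "prompt treatment with IV methylprednisolone 2 to 4 mg/kg/day started".
- Second line: "If still no improvement within 2 to 3 days despite 1 to 2 mg/kg IV methylprednisolone, promptly start immunosuppressives such as infliximab".

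**Hepatitis in HCC patients, second transaminase level.** This level covers an isolated AST or ALT above 5 and up to 8 times ULN if normal at baseline, or above 2 times baseline and up to 12.5 times ULN if elevated at baseline.
- First steroid: prednisone 1 to 2 mg/kg/day, oral or IV equivalent, is recommended if the event persists or worsens and is suspected to be immune-mediated.
- With no improvement after 2 to 3 days: "consider additional workup and treatment with IV methylprednisolone 2 to 4 mg/kg/day".
- Next step: "If still no improvement within 2 to 3 days despite 1 to 2 mg/kg/day of IV methylprednisolone, consider additional abdominal workup". The same sentence goes on to suggest considering mycophenolate.

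The general considerations at the start of Appendix F present the whole table as recommended management.

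**The concern.** A stepwise rule has to say what failed before the next step begins. In these two rows the trigger names IV methylprednisolone at 1 to 2 mg/kg, but the step before it names 2 to 4 mg/kg/day. The lower range appears earlier in each row only as prednisone or an unspecified IV equivalent. A clinician reading the trigger sentence alone cannot tell whether failure is judged after the 2 to 4 mg/kg/day step or before it.

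At stake are the steroid dose at which a patient counts as refractory and the point at which infliximab or mycophenolate comes in. The topic is not marginal. Section 3.4.2.5 describes diarrhea/colitis as the most common treatment-emergent SAE with tremelimumab alone, and it sends the reader to Appendix F. All planned patients are to receive tremelimumab, and safety is the secondary objective (section 1.1.2).

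**Working it through.** No sample-size or error-rate formula applies, and the plan states no figure to reproduce. The check compares, for each Appendix F ladder that restates a methylprednisolone dose, the dose in the step with the dose in the next trigger.

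| Appendix F row | Dose in the step (mg/kg/day) | Dose in the next trigger (mg/kg/day) | Same? |
|---|---|---|---|
| Pneumonitis, grade 2 | 2 to 4 | 2 to 4 | yes |
| **Diarrhea/colitis, grade 2** | **2 to 4** | **1 to 2 (no per-day unit given)** | **no** |
| Hepatitis (non-HCC), grade 2 | 2 to 4 | 2 to 4 | yes |
| Hepatitis (non-HCC), grade 3 or 4 | 1 to 2 | 1 to 2 | yes |
| **Hepatitis in HCC, second level** | **2 to 4** | **1 to 2** | **no** |
| Hepatitis in HCC, third level | 1 to 4 | 1 to 4 | yes |
| Myocarditis, grade 2 to 4 | 2 to 4 | 2 to 4 | yes |
| Myositis, grade 2 | 2 to 4 | 2 to 4 | yes |
| Myositis, grade 3 or 4 | 2 to 4 | 2 to 4 | yes |

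The two closest parallels show the consistent form. Grade 2 pneumonitis has "If still no improvement within 2 to 3 days despite IV methylprednisolone at 2 to 4 mg/kg/day", and grade 2 non-HCC hepatitis has "If still no improvement within 3 to 5 days despite 2 to 4 mg/kg/day of IV methylprednisolone". Each follows a step at that same dose.

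**Size of the mismatch.** Trigger divided by step is 1/2 = 0.5 at the lower end and 2/4 = 0.5 at the upper end. The two ranges meet only at 2 mg/kg. As an illustration, take 75 kg, the weight implied by section 1.2.10, which equates 75 mg with 1 mg/kg. The trigger range is then 75 × 1 to 75 × 2 = 75 to 150 mg/day, and the step range is 75 × 2 to 75 × 4 = 150 to 300 mg/day.

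**Timing, from the intervals printed in the rows.**
- If the trigger refers to the step just before it, a patient has 2 to 3 days on the first steroid plus 2 to 3 days on 2 to 4 mg/kg/day. Second-line therapy comes about 4 to 6 days after the first steroid.
- If the trigger is taken literally, assume the first steroid was IV methylprednisolone at 1 to 2 mg/kg/day, given as the IV equivalent. The condition can then be met after 2 to 3 days. At that moment two instructions apply together: step up the steroid, and start (colitis) or consider (HCC) a second immunosuppressive.
- The difference is one step, or 2 to 3 days.

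**The case against.** The strongest reply is that the rows are read in order. The trigger opens with a condition of *still* no improvement and comes straight after the 2 to 4 mg/kg/day step. The preceding bullet already covers failure on the first steroid and says what follows. A patient who has failed 2 to 4 mg/kg/day has also failed 1 to 2 mg/kg/day, so in sequence the mismatched dose changes nothing. In the HCC row both the higher steroid dose and the immunosuppressive are only to be considered, with a hepatology consult recommended. In the colitis row a gastroenterology consult comes first, and a worsening patient is managed as grade 3 or 4.

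Most of this stands. The sequential reading is the likelier one, and a directive conflict exists only in the colitis row. It does not remove the ambiguity, for two reasons. The first step allows an IV equivalent, so a patient may already be on IV methylprednisolone near the trigger dose. And the grade 3 or 4 colitis row just below goes from methylprednisolone 1 to 2 mg/kg/day to adding infliximab with no 2 to 4 mg/kg/day step, so the literal reading is not foreign to the appendix.

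A reader might go further and infer that sites will diverge, that 40 of 70 planned patients are affected, or that drug resumption and the immune read-outs are distorted. The documents do not support these inferences.
- Sections 3.7.1 and 12.5.3 describe care at one centre, and section 7.4.1 describes one team meeting weekly to discuss each patient.
- The HCC cohorts total 10 + 30 = 40 of 70, but that counts patients to whom the row could apply, not patients expected to reach the trigger.
- The rule for resuming study drug (recovery to the stated level plus a completed steroid taper) is the same on either reading. In colitis the taper alone is at least 28 days, against a shift of 2 to 3 days.
- No effect on the immune assays is shown.

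**Conclusion.** The inconsistency is real and confined to two rows. In each, the dose at which failure is judged is half the range named in the preceding step, and no earlier step of the row names it as IV methylprednisolone. The practical consequence is modest: second-line immunosuppression could start one step (2 to 3 days) earlier. That rests on a literal reading and on the assumption that the first steroid was given as IV methylprednisolone.

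How often this would arise cannot be sized. The documents give no rate for steroid-refractory grade 2 colitis or for the second transaminase level. The nearest figures are poor proxies: colitis of any grade in 28 of 3006 patients (0.9%) on durvalumab alone (Appendix G), and one colitis among three discontinuations for immune-related events in the earlier 41-patient study (section 1.2.10). The remark in section 3.4.2.5 concerns serious events on tremelimumab alone and does not fill the gap.

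The 6-month PFS endpoint, the power statement and the tabulation of adverse events in section 10 are untouched. The point is still worth correcting because it sits in an operative toxicity instruction that should be readable in only one way. Whether the mismatch came from the manufacturer's guideline dated 14 October 2020 or from transcription cannot be told from these documents.

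**What to change.** In the grade 2 diarrhea/colitis row and in the second transaminase level of the HCC hepatitis guidance, reconcile the trigger sentence with the step before it, so that each row states one dose at which failure is judged. Supply the missing per-day unit in the colitis trigger at the same time. Check both sentences against the manufacturer's guideline first. Which dose is right is for the sponsor and manufacturer to decide, and this review takes no position on it.

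The cost is two sentences, by amendment or clarification letter to the treating team. No procedures, visits or patients are added, and no analysis changes.
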